8.2 Study Drug Packaging, Labeling, and Storage

Study drug for the placebo-run in phase of the study will be provided in a 14-day treatment kit. The treatment kit will include 42 pouches. Each pouch will contain one vial. Each vial is intended for dosing once (one drop in each eye and not used again). The label on the kit and pouch will minimally contain the following information: Study ID, kit number, storage temperature, and "Caution: New Drug – Limited by Federal Law to Investigational Use. Keep out of reach of children".

Study drug for the double-masked phase of the study will similarly be provided in two 14-day treatment kits which are labeled and packaged identically to supplies used in the run-in period. Each 14-day treatment kit will include 42 pouches. Each pouch will contain one vial. Each vial should be used for one dose (one drop in each eye) and not used again. The label on the kit and pouch will minimally contain the following information: Study ID, kit number, storage temperature, and "Caution: New Drug – Limited by Federal Law to Investigational Use. Keep out

of reach of children." There will be no labeling on the individual vials of study medication due to size.

Storage of study drug at the study site must be under locked and secure conditions with limited staff access. Study medication for the run-in and treatment phase must be stored at the site between 2 – 8°C (36 - 46°F). The subject may store the drug at ambient conditions (between 15°C and 25°C (59°F to 77°F), but they must be instructed to store study drug in a secure place at room temperature, away from environmental extremes, and out of the reach of children.

At the end of the study, all study materials, including unused study medication bottles will be returned to Parion Sciences, Inc. (or its designee) for destruction. The study monitor or designee should verify drug accountability at routine monitoring visits.

8.3 Treatment Administration and Dosing Instructions

Subjects will be instructed on how to instill study medication into each eye and to conduct three instillations on each eye daily.(Appendix III). At Visit 1, the first dose will be administered by the subject under the supervision of trained site personnel who may offer advice/correction on the instillation technique as necessary. At Visit 1 all subjects will receive single-masked placebo for up to 14 days. Only the site personnel and not the subject will know the study medication is placebo.

At Visit 2, eligible subjects will be randomized to receive either 0.017% P-321 Ophthalmic Solution, or Placebo in a 1:1 ratio for the duration of the trial. The first dose from the newly assigned treatment kit at Visits 2 and 3 will be self-administered by the subject in the clinic under the supervision of trained site personnel who may offer advice/correction on the instillation technique. During the double-masked treatment period, neither the subjects nor site personnel will know which treatment the subject receives at which visit. Subjects will administer treatment TID, and to enhance compliance should administer around an event so that it may be easier to remember, such as eating. However food is not required at administration.

At Visit 4, no new study medication will be dispensed and no further instillation of study drug is required.

8.4 Randomization, Study Masking, and Dispensing Instructions

8.4.1 Single-Masked Placebo for Placebo Run-In Period

For the single-masked placebo run-in period, subjects will be dispensed a two-week supply of placebo vehicle in a treatment kit that is identical in appearance to the double-masked treatment kit that will be dispensed at subsequent visits. Each treatment kit will contain 42 pouches with a single vial of study drug included in each pouch.

8.4.2 Double-Masked Treatment Period

Eligible subjects will be randomized in a double-masked manner once they have met all Randomization criteria (Section 6.3). Subjects will be randomized in a 1:1 ratio to P-321 Ophthalmic Solution 0.017% or Placebo (vehicle), stratified by clinical site. The randomization code will be generated by an independent designee of Parion Sciences, Inc. who is not involved in the day-to-day conduct of the clinical study. The randomization code will be provided to the

designee of Parion Sciences, Inc. who is responsible for the packaging and labeling of the clinical supplies for each clinical site.

The study drug supplies will be labeled with sequential treatment numbers. Subjects will be assigned the next available treatment number upon qualifying to be randomized. Double-masked study medication for each subject will be packaged, labeled and supplied to the study site in one kit per subject. The carton will contain two boxes, each box will contain a two-week supply of study drug. Each 2-week supply box will contain 42 identical pouches with a single vial of study drug in each pouch.

The randomization codes will be maintained in a secure location separate from the study investigator. All study personnel directly associated with the conduct of the clinical study, including the investigator, medical monitor, study site personnel, subjects in the study and those involved in the conduct of the study will remain masked to double-masked study treatment assignments.

8.5 Release of Clinical Study Supplies to the Investigator

Parion or Parion's designee's standard operating procedures for releasing clinical trial supplies to the site will be followed.

8.6 Treatment Compliance

Treatment compliance will be assessed based on medication accountability performed by the site staff. Subjects will be asked to return used and unused study drug for this purpose. Study medication accountability will be recorded on a log and compliance will be calculated. Appropriate subject investigation and counseling should occur if discrepancies arise in expected vs returned study drug. The time and date of the in clinic study drug administrations, the screening and treatment number will be captured in the CRF.

Compliance will also be reinforced by study personnel during the visits and between visit phone calls.

8.7 Study Drug Accountability

Study medication accountability will occur during monitoring visits by Parion Sciences, Inc, or its designee. Accountability will be ascertained by performing reconciliation between numbers of kits/vials of study medication received on site, number of kits/vials dispensed to subjects according to the protocol-specified dosing regimen, and the remaining unused study medication at the time of reconciliation.

Clinical trial materials will be shipped to the investigational site under sealed conditions. Study medication shipment records will be verified by comparing actual quantity of drug received against the shipment inventory sheet accompanying the drug received at the site. Accurate records of receipt and disposition of the study medications (e.g., dates, quantity, subject number, dose dispensed, returned, etc.) must be maintained by the investigator or his/her designee.

At the end of the study, all study materials, including used and unused study medication vials and kits will be returned to Parion Sciences, Inc. or designee for destruction, once authorized. The study monitor or designee should verify drug accountability at routine monitoring visits.

8.8 Procedure for Breaking the Randomization Code

The randomization code may not be broken except in the case of a medical emergency, or occurrence of an SAE. In case of a medical need, the investigator will treat the subject as needed regardless of randomized treatment. Since there is no specific antidote to P-321 Ophthalmic Solution, immediate emergency unmasking is generally not warranted. If the investigator feels it is necessary to unmask a subject's treatment assignment after an emergency situation, the investigator must call the medical monitor and notify Parion Sciences, Inc. The treatment assignment will be revealed on a subject-by-subject basis, leaving the masking of the remaining subjects intact.

In the absence of medical need, the randomization code will not be available to the above personnel until after the study is completed and the database is locked.

8.9 Concomitant Medications

8.9.1 Medications Permitted

All medications including prescription, over-the-counter, and natural remedies, that the subject has taken within 28 days prior to Visit 1 or during the study will be recorded in the CRF and in the subjects' source documents. The name of the drug, dose, route of administration, duration of treatment (including start and stop dates), frequency, and indication will be recorded for each medication. Fluorescein, lissamine green, and topical ocular anesthetics used in study procedures do not need to be recorded on the concomitant medications page.

Subjects taking the following medications may continue to take these medications during the study provided they are taking them at stable doses (as needed [PRN] doses are not permitted) and have been on them for at least 28 days prior to the Visit 1. Subjects taking other concomitant medications at stable doses may be eligible for inclusion with Medical Monitor approval.

- a. contraceptives (oral and transdermal)
- b. antihypertensives
- c. drugs for heart failure or angina
- d. thyroid or hormone replacement therapy
- e. anticoagulants
- f. benzodiazepines
- g. any nutritional supplement containing Omega-3 acids (eg, fish oil and Flax Seed oil)

8.9.2 Medications Not Permitted

The following medications are explicitly excluded for 14 days prior to Screening and throughout the study:

- a. Any topical prescription or OTC ocular medication including topical cyclosporine (e.g. Restasis $^{\textcircled{\$}}$), lifitegrast (Xiidra $^{\textcircled{\$}}$), or topical anti-glaucoma medications. Diagnostic solutions are exempt.
- b. Ocular, intranasal or systemic corticosteroids or other immunomodulatory or immunosuppressive medications

- c. Topical ocular or systemic antibiotics, including doxycycline or tetracycline analogs
- d. Oral or topical secretagogues such as pilocarpine and cevimeline (Evoxac®)
- e. Systemic medications with known significant anticholinergic pharmacologic activity as referenced in the Prohibited Medication List for the study, such as tricyclic antidepressants. Selective Serotonin Re-uptake Inhibitors (SSRIs) are permitted if patient is on stable dose for 28 days prior to Visit 1 and during the study.

The following medications are explicitly excluded for 14 days prior to Randomization Visit and throughout the study:

- a. Nasal, ocular, or oral antihistamines
- b. NSAIDs and aspirin use with the exception of low dose (81mg) aspirin per day
- c. Topical autologous serum
- d. Lubricant eye drops

9 Assessment of Efficacy

Efficacy will be assessed by evaluation of symptoms and signs. Specific procedures for conducting these assessments will be provided in the Study Manual. Where relevant, it is imperative that ocular assessments be conducted in a specified order, first in the right eye and then in the left eye.

9.1 Symptom Assessments

The primary efficacy endpoint and several of the secondary efficacy endpoints in this study are derived from subjective subject-completed symptom questionnaires. Therefore, it is critical that these questionnaires are completed in the specified order, according to specific instructions, and in a setting where the subject has minimal distractions and sufficient time to complete them. After completion of these questionnaires, the study coordinator, unless specifically prohibited by instrument instructions, should review the responses for completeness only.

Symptoms will be assessed at every visit (Visits 1-4 and/or Early Termination) before any other study procedures have been conducted. The symptom questionnaires are commonly used instruments in dry eye trials and are described in Appendix IV.

The subject will be given the questionnaires to complete in the following order:

- SANDE (Part 1 completed at Visits 1-4 and Part 2 completed at Visits 2-4). SANDE Part 1 scores must be >20 but less than 90 for both symptom frequency and symptom severity to be eligible for randomization (Section 6.3)
- SPEED
- 7-item symptom questionnaire

If collected on paper, original subject responses from these symptom questionnaires will be retained in the source documents and results will be transcribed from these source documents onto the CRF and verified that it has been transcribed correctly.

9.2 Assessment of Signs

9.2.1 Tear Collection for Biomarkers of Inflammation

Tear collection for biomarkers of inflammation will be assessed in both eyes at Visits 2, 3, and 4. Tear collection must be done under the slit lamp by the Investigator before any staining of the eye has occurred. Tears collected will be assessed for prostaglandins (from the Study Eye) and MMP-9 activity (from the Fellow Eye). Information on collection procedures, sample handling, labeling and storage is provided in the Study Manual.

9.2.2 TBUT

[figure not shown]
TBUT will be assessed in both eyes at Visits 1-4 in OD first, then OS. The procedure and information on staining is provided in the Study Manual.

9.2.3 Corneal Staining, Bulbar Conjunctival Staining, and Lid Wiper Staining

The assessment of corneal staining, bulbar conjunctival staining and staining of the lid wiper region of the upper eyelid will be assessed first in the right eye and then the left eye using

fluorescein 2% and lissamine green 1%. Corneal and conjunctival staining scores must be within certain limits at Visit 1 and Visit 2 in order for the subject to be eligible for randomization (Section 6.3). Timing of these assessments is specified in Figure 2. Photographs of lid wiper staining will be taken if technology is available. Additional detailed specific instructions related to each of these assessments will be provided in the Study Manual.

Figure 2 Sequence of Ocular Assessments

9.2.4 Impression Cytology

Impression cytology (with anesthesia) will be performed on the Study Eye only at Visits 2 and 4 per the procedures outlined in the Study Manual.

9.2.5 Other Assessments

In addition of the asssessments indicated in Sections 6.1 and 6.2, additional assessments will be done at Screening Visit 1 only to characterize the study population, including IOP, Schirmer's test, assessment of tear osmolarity and clinical assessment of the Meibomian glands, consisting in evaluation of plugging, character of secretion, and expressibility of the Meibomian glands complemented with meibography to assess Meibomian gland loss if technology is available at the site. Additional information about the procedures for these assessments are provided in the Study Manual.

10 ASSESSMENT OF SAFETY

Subject safety will be evaluated by a medical professional during the study. Tolerance of study medication as well as general subject well-being will be assessed. Subjects may be discontinued from the study at any time by the investigator if this action is considered in the subject's best interest.

Safety will be assessed by:

- Adverse events
- BCVA
- Biomicroscopy and external eye examination
- Physical examinatons
- Vital signs
- Clinical laboratory tests

10.1 Adverse Event Reporting

An AE is any untoward medical occurrence in a subject or clinical investigation subject administered a pharmaceutical product, which does not necessarily have to have a causal relationship with this treatment. AEs will be documented upon signing the informed consent. A treatment emergent AE (TEAE) is an AE that either commenced following initiation of double-masked study treatment or was present prior to double-masked study treatment but subsequently increased in frequency or severity following initiation of the double-masked treatment.

All AEs will be collected from the time ICF is signed and study procedures have started until the following time points:

- For subjects who are not randomized until time of screen failure (e.g., screen failure, withdrawal of consent)
- For enrolled subjects who have the Follow-up Telephone Call: through the Follow-up Telephone Call
- For subjects who Early Terminate from the study: through the Early Termination Visit.

All subjects will be queried, using non-leading questions, about the occurrence of AEs at each study visit. When possible, a constellation of signs and/or symptoms will be identified as 1 overall event or diagnosis. All AEs for enrolled subjects (those subjects who receive single-masked run-in and or double-masked medication) will be recorded in the CRF and source document. The following data will be documented for each AE:

- Description of the event
- Classification of "serious" or "nonserious"
- Date of first occurrence and date of resolution (if applicable)
- Severity
- Causal relationship to study drug(s)

Parion Sciences, Inc.
Protocol P-321-202 Amendment 01

- Action taken
- Outcome
- Concomitant medication or other treatment given

If an AE occurs, the investigator will institute and/or support treatment as deemed appropriate. If a non-serious AE is unresolved at the time of the last visit, a reasonable effort will be made to follow up until the AE is resolved or stabilized, the subject is lost to follow-up, or there is some other resolution of the event.

There are many symptoms associated with dry eye that can vary in intensity and frequency over time. Only symptoms that worsen or become more frequent, in the opinion of the subject and outside of their normal experience, should be reported as an adverse event.

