
Number of Subjects Randomized:	Number of Centers:
Approximately 65 randomized to complete 60 subjects	Approximately 7
Test Product and Doses:	Route of Administration:
0.017% P-321 Ophthalmic Solution	Ocular instillation, one drop per eye TID for 28 days
Reference Product and Doses:	Route of Administration:
Placebo (vehicle)	Ocular instillation, one drop per eye TID for 14 days in the run-in period and for 28 days in the double-masked treatment period

Duration of Treatment:

Eligible subjects will receive placebo TID in both eyes from Visit 1 and through the evening before Visit 2 (for 14 days). Starting at Visit 2 (Randomization – Treatment Day 1) and continuing through the day before Visit 4, subjects will receive 0.017% P-321 Ophthalmic Solution or Placebo TID in both eyes. A follow up call will be scheduled 5-9 days after the Visit 4. Total duration of the study is expected to be approximately 50 days including placebo-run-in, treatment and follow up. Three phone calls to remind subjects of dosing regimen and to inquire about adverse effects will also be done during the study and will occur between Visits 1 and 2, Visits 2 and 3, and Visits 3 and 4.

Criteria for Evaluation:

This study will evaluate the efficacy and safety of P-321 Ophthalmic Solution and Placebo in subjects with dry eye. Background characteristics will be evaluated to better characterize subjects at entry including: demographics, BCVA, dry eye symptoms upon entry, osmolarity, meibography (if available), meibomian gland evaluation, Screening IOP and Schirmer's test, medical history, and concomitant medication use.

Efficacy

Symptoms and signs will be assessed throughout the study. Symptoms will be assessed by subject-reported symptom questionnaires (SANDE and SPEED questionnaires and a 7-item symptom questionnaire). Signs will be assessed by staining of the cornea, bulbar conjunctiva, the lid wiper region of the upper eyelid and by TBUT. Exploratory assessments will include biomarkers of inflammation in tears and from impression cytology samples collected from the lid wiper and the bulbar conjunctiva.

Safety

Safety will be assessed throughout the study by adverse event monitoring, biomicroscopy and external eye examination, BCVA, physical examinations, vital signs, drop instillation comfort assessments, and clinical laboratory tests.

Statistical Analysis:

Sample Size

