6.5 Subject Withdrawal Criteria

Treatment may be discontinued and the subject withdrawn at any time during the study at the discretion of the investigator, Medical Monitor or Parion Sciences for any reason including but not limited to occurrence of an AE which precludes subsequent participation, withdrawal of Informed Consent, or requirement of an ocular surgery or intervention. Also in the event that a woman becomes pregnant while participating on the study, she will be withdrawn from the study and followed to resolution (i.e., birth or voluntary or spontaneous termination of the pregnancy) (Section 10.2). In the event that discontinuation of treatment is necessary, the investigator will make every attempt to complete all subsequent safety assessments. The reason for premature discontinuation should be documented. Subjects who withdraw from the study will not be replaced.

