7.9 Early Termination Visit

The purpose of the Early Termination visit is to obtain critical information about the subject's participation, and should be scheduled preferably before there has been a substantial lapse in study medication usage. However, even if there has been a medication lapse, the subject should be encouraged to return to the clinic for this visit, and should be instructed to return all study medication. The following assessments will be performed at the Early Termination Visit for randomized subjects who are withdrawn from the study prematurely:

- Collect previous study medication supplies from subject
- Document reason for early termination
- Document date and time of last dose of study medication
- Assess adverse events since the last visit and during this visit
- Assess concomitant medications and medical changes since last visit
- Collect vital signs (pulse, blood pressure, temperature and respiration rate), and weight
- Abbreviated physical exam (including EENT, respiratory, cardiovascular, musculoskeletal, gastrointestinal, and dermatological)
- Biomicroscopy and external eye examination
- Collect blood for Hematology and Chemistry
- Urine pregnancy test (women of child-bearing potential only)

Once these assessments have been complete, the subject may be discharged from the study, provided that there is no need for additional follow-up to continue to monitor an adverse event or other condition.

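### For early terminators, AE collection ends at the Early Termination Visit with no later call, so AEs that start after that visit are missed; the expected effect is small and the remedy cheap

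*Protocol*

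**What the plan says.** Protocol 10.1 sets three ends to AE collection:

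- Not randomized: "For subjects who are not randomized until time of screen failure".
- Subjects who have the call: "For enrolled subjects who have the Follow-up Telephone Call: through the Follow-up Telephone Call".
- Early terminators: "For subjects who Early Terminate from the study: through the Early Termination Visit".

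The call exists only in relation to Visit 4. The synopsis states "A follow up call will be scheduled 5-9 days after the Visit 4", and section 7.8, Appendix I and the SAP schedule (SAP 1.2) agree. Dosing in the double-masked period runs from Visit 2, "continuing through the day before Visit 4".

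Section 7.9 does not fix a day for the ET Visit. It "should be scheduled preferably before there has been a substantial lapse in study medication usage", although subjects are encouraged to attend even after a lapse. AEs are assessed at the visit. The subject may then be discharged, "provided that there is no need for additional follow-up to continue to monitor an adverse event or other condition". No further contact is scheduled.

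Section 6.5 says that when treatment has to be discontinued, "the investigator will make every attempt to complete all subsequent safety assessments".

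SAP 5.3.1 summarises AEs as frequencies and percentages. The Safety Population (Protocol 11.1, SAP 4.2) is everyone who took at least one double-masked dose. The SAP definition of a treatment-emergent AE in the double-masked period (3.3.7) has no closing date, and no exposure adjustment is described.

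**The concern.** A completer is asked about AEs once more after treatment has stopped. An early terminator is not, yet counts as a full subject in the denominator. An AE that begins after the ET Visit has no scheduled route into the database, whereas the same AE in a completer would be picked up at the call and counted.

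If early termination is unequal between arms, so is the amount of post-treatment AE capture, and the arm with more terminations tends to look slightly better tolerated. Safety and tolerability is a secondary objective, and an AE is one of the listed reasons for withdrawal in 6.5, so the affected subjects are relevant to that comparison.

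There is also a practical ambiguity. Section 6.5 asks sites to pursue later safety assessments after discontinuation, while 10.1 closes AE collection and 7.9 allows discharge. A site that learns of a new AE a few days after the ET Visit cannot tell from the text whether to record it.

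**Working it through.** **1. The plan's own duration.** Run-in 14 days (Protocol 7.1), treatment 28 days, call 5-9 days after Visit 4. 14 + 28 + 5 = 47 and 14 + 28 + 9 = 51 days elapsed. At the nominal 7 days this is 49 elapsed, or 50 counted inclusively. That reproduces the approximately 50 days in 5.3, a figure that includes the call and so describes a completer.

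**2. Completers' capture after the last dose.** Last dose Day 28, Visit 4 Day 29. The call falls on Day 29 + 5 = 34 to Day 29 + 9 = 38. Capture after the last dose is 34 − 28 = 6 to 38 − 28 = 10 days.

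**3. Early terminators' shortfall.** Let g be the days from last dose to ET Visit. Capture after the last dose is g, so the shortfall is (6 to 10) − g. The protocol does not give g; the values below are assumed.

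| g (days) | Shortfall against completers (days) |
|---|---|
| 0 | 6 to 10 |
| 1 | 5 to 9 |
| 3 | 3 to 7 |
| 5 | 1 to 5 |
| 7 | −1 to 3 |
| 10 | −4 to 0 (none) |

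The timing preference in 7.9 points to the upper rows.

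**4. Subjects affected.** Protocol 11.2 and SAP 3.1 assume 10% dropout before Visit 3: 0.10 × 65 = 6.5, about 6-7 subjects. This is dropout for any cause and excludes terminations after Visit 3. It is not a count of AE withdrawals.

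**5. Effect on crude incidence.** Let d be the fraction of an arm that terminates early, and q the probability that such a subject's first new AE falls only in the missed window. The loss in that arm's incidence is q × d. Neither input is in the documents except the 10% dropout, so I assume q = 2-10% and d = 10-30%, with 65 / 2 = 32.5 subjects per arm.

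- Low end: 0.02 × 0.10 = 0.2 percentage points; 32.5 × 0.002 = 0.07 subject.
- Middle: 0.05 × 0.20 = 1.0 point; 32.5 × 0.01 = 0.33 subject.
- High end: 0.10 × 0.30 = 3.0 points; 32.5 × 0.03 = 0.98 subject.

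These are losses within one arm. The distortion of the comparison is the difference between arms: with q = 5%, and d = 20% in one arm and 10% in the other, it is 1.0 − 0.5 = 0.5 percentage points.

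**6. What a call would change.** Take a last dose on Day 7 and an ET Visit on Day 8. Collection now ends on Day 8. With a call 5-9 days later it would end on Day 13-17, which is 6-10 days after the last dose and matches completers on that measure. It would still stop well before Day 34-38.

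**The case against.** The strongest reply is that the most informative event is not lost. The ET Visit asks about AEs and includes biomicroscopy, a physical examination and laboratory tests. Discharge is conditional on no AE needing monitoring (7.9), unresolved non-serious AEs are followed past the last visit (10.1), and serious AEs are followed to resolution (10.1.1). AEs leading to discontinuation have their own table. A subject withdrawn for a treatment-emergent AE is therefore already counted in any overall incidence; only further preferred terms could be missed. All of this stands. It does not cover AEs that begin later, because following a known event does not prompt anyone to look for a new one.

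A reader might infer several stronger things that the documents do not support:

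- **That the reaction causing withdrawal is under-captured.** It is not, for the reasons just given.
- **That early terminators are the subjects most likely to have reacted.** This is plausible, but 6.5 also lists consent withdrawal, ocular surgery and discretionary reasons, and no split by reason is given.
- **That every early terminator loses a fixed window.** The loss depends on an ET date that the protocol leaves open.
- **That 6.5 flatly contradicts 10.1.** Section 6.5 can be read as covering subjects who stop the drug but stay in the study, and the second rule in 10.1 would include them if they have the call. But 6.5 also speaks of the subject being withdrawn, so the wording is loose and needs clarifying.

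The yield of an off-drug call may also be low. Animal ocular irritation reversed on stopping (3.2.3), and the 0.01% clinical experience showed no systemic availability (7.11). On the other side, the rabbit data in 3.2.2 give a tear half-life of about 24 hours and sustained conjunctival and eyelid levels for up to 48 hours after one dose, so drug could still be on the ocular surface at an early ET Visit. Neither set of data settles the question.

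**Conclusion.** The asymmetry is real and nothing elsewhere in the protocol or SAP closes it. It is confined to AEs with new onset after the ET Visit. The shortfall is up to 6-10 days when that visit closely follows the last dose and disappears at a gap of about 10 days.

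The expected effect is small: 0.2 to 3.0 percentage points of an arm's crude incidence, or about 0.1 to 1 subject per arm. That range rests on assumed event rates of 2-10% and assumed termination rates of 10-30%. The direction, slightly favouring the arm with more early terminations, holds only if termination is in fact unequal.

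This is a cheap improvement to safety data collection. It does not affect efficacy and does not undermine the safety comparison as a whole.

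**What to change.** Amend Protocol 10.1, 7.8 and 7.9 so that early terminators who can be reached have AEs collected through the existing follow-up call, made 7 ± 2 days after the ET Visit. Carry the change into Appendix I and the SAP schedule (SAP 1.2). In the same amendment, reconcile 6.5 with 10.1 by stating which later safety assessments apply to a subject who stops treatment and which to one who leaves the study.

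The cost is one extra call per early terminator by existing site staff: about 6-7 if the 10% dropout before Visit 3 holds, more if there are later terminations, fewer where subjects cannot be reached. The text changes are small but need IRB approval under 15.1.

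The call makes the post-visit window 5-9 days for both groups. It does not equalise total AE follow-up, because most of an early terminator's shorter follow-up comes from leaving before Day 29. The safety tables should be read with that in mind.
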